7.4 Criteria for Discontinuation or Withdrawal of a Subject

The primary reason for discontinuation or withdrawal of the subject from the study should be recorded in the [electronic] case report form ([e]CRF) using the following categories. For screen or baseline failure subjects, refer to Section 9.1.13.

1. Pretreatment event (PTE) or adverse event (AE). The subject has experienced a PTE or AE that requires early termination because continued participation imposes an unacceptable risk to the subject's health or the subject is unwilling to continue because of the PTE or AE. For guidance on withdrawal criteria due to AESIs please refer to Section 10.2.1.3.

CONFIDENTIAL

2. Liver Function Test Abnormalities

Based on local country criteria, subjects in a clinical trial who experience ALT and/or AST $>3 \times \text{ULN}$ and total bilirubin $>2 \times \text{ULN}$ and satisfy the following two criteria: (1) the liver injury is hepatocellular in nature and there is not a prominent cholestatic component; (2) there is no more likely alternative cause than drug induced liver injury, such as acute viral hepatitis A or B, or other acute liver disease;

If ALT or AST $>3 \times \text{ULN}$, laboratory tests should be repeated within a maximum of 7 days, and preferably within 48-72 hours. If the ALT or AST remains elevated $>3 \times \text{ULN}$ on these 2 consecutive occasions, and this observation cannot be explained by concomitant disease or another alternative etiology, the abnormality should be recorded as an AE. The investigator must contact the Medical Monitor for consideration of immediate discontinuation of study medication, discussion of the relevant subject details and possible alternative etiologies.

In addition, study medication should be discontinued immediately with appropriate clinical follow-up, including repeat laboratory tests, until a subject's laboratory profile has returned to normal, if the following circumstances occur at any time during study medication treatment:

- ALT or AST $>8 \times \text{ULN}$.
 - ALT or AST $>5 \times \text{ULN}$ and persists for more than 2 weeks.
 - ALT or AST $>3 \times \text{ULN}$ in conjunction with elevated total bilirubin $>2 \times \text{ULN}$ or international normalized ratio (INR) >1.5 .
 - ALT or AST $>3 \times \text{ULN}$ with appearance of fatigue, nausea, vomiting, right upper quadrant pain or tenderness, fever, rash and/or eosinophilia ($>5\%$).

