AE Assessment	Visit 2, Visit 3, every 6 and 12 month visit after randomization, every 3 and 9 month phone visit, Unscheduled Visit, EoS/EW Visit and follow up visit	Investigator/ Sub-Investigator
C-SSRS	Visit 3, every 6 and 12 month visit after randomization, EoS/EW Visit, and follow up visit	Certified tester

(a) May be administered prior to the Cognitive Test Battery only during the baseline visit.

(b) Sites may utilize the same Investigator/Sub-Investigator tester administering the CDR for the ADCS-CGIC-MCI.

(c) May be administered in parallel with other assessments.

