In general, the baseline value for a variable is defined as the last observation prior to the first dose of double-blind study medication (visit date \leq first dose date), including the screening value, if necessary.

Adverse events that start more than 30 days after the last dose of double-blind study medication (start date – last dose date >30) will be listed, but excluded from the summaries and analyses. For efficacy and other safety data, data that are obtained more than 7 days after the last dose of double-blind study medication (visit date – last dose date > 7) will be listed, but excluded from summaries and analyses. (Note: This efficacy data window only applies to determining which data are included/excluded from the summary statistics and formal statistical analysis tables for a given efficacy endpoint. All events of MCI due to AD (or AD dementia) as determined by the adjudication committee will be included in the time-to-event analyses, without regard to the date of last dose of double-blind study medication.)

If the date of first dose of double-blind study drug collected in the eCRF is missing, then for summary purposes the day after the first dispense date will be used as an estimate for the date of first dose. However, if all dispensed study drug is returned, then the subject is assumed to have not taken any study drug, and the first dose date will not be imputed.

If the date of last double-blind study drug dose collected in the eCRF is missing, then the earliest of the following dates will be used for the last dose date for analysis and summary purposes: date of death, date of last visit (recorded in the eCRF), last double-blind study drug return date, and the last double-blind study drug dispense date (following the last drug return date) + 200 days (ie, the double-blind study drug dispensing interval corresponding to the number of study drug tablets dispensed).

The study window convention will not be applied to the eCRF data listings. The data listings for eCRF data will display the raw data as collected and entered in the eCRF. For efficacy listings, windowed visits will also be shown on the listings.

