9.14 Safety Analysis

Safety summaries will be based on the safety set. Safety summaries will include descriptive statistics for values, changes, and incidence of events for all treatment groups combined in addition to summary by treatment group. Conventions for the definition of baseline values and visit windowing are provided in Section 9.1.3. Missing safety data will not be imputed.

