9.14.1 Adverse Events

All adverse events will be coded using the latest version of MedDRA. In this dictionary, each verbatim term is coded to a lower level term, and then mapped to a preferred MedDRA term, which is then mapped to an SOC. All adverse events will be included in the data listings but only treatment-emergent adverse events will be included in the summary tables.

A treatment-emergent adverse event (TEAE) is defined as an adverse event with an onset that occurs after receiving study drug (AE start date \geq first dose date) and within 30 days after receiving the last dose of study drug (AE start date – last dose date ≤ 30). A TEAE may also be a pretreatment adverse event or a concurrent medical condition diagnosed prior to the date of first dose of study drug that increases in severity after the start of dosing. Adverse events data with onset occurring more than 30 days after last dose of study drug (AE start date – last dose date > 30) will be listed, but not included in the summary tables. Adverse events with missing onset dates will be summarized regardless of severity and relationship to study medication.

Serious adverse events (SAEs) with onset that occurs after receiving study drug (AE start date \geq first dose date) and within 30 days after receiving the last dose of study drug (AE start date - last dose date ≤ 30) will be summarized.

At the adverse event level, the summary tables will present the number of subjects reporting each of these MedDRA events, ie, the number of subjects reporting one or more events which map to the given MedDRA term.

At the SOC level, the summary tables will present the number of subjects reporting one or more events that map to the given SOC. That is, the number of subjects reported at the SOC level will be less than or equal to the sum of the subject counts across all adverse events within that SOC.

In selected summaries (TEAEs overview, and TEAEs by SOC and preferred term), adverse events will be summarized by the number of events reported in addition to the number and percentage of subjects with events.

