9.14.2 Clinical Laboratory Evaluations

The following clinical laboratory parameters will be summarized:

- Serum chemistry including alanine aminotransferase (ALT), alkaline phosphatase, aspartate aminotransferase (AST), total bilirubin, GGT, total protein, albumin, creatinine, blood urea nitrogen (BUN), potassium, sodium, glucose, calcium, vitamin B12, folate, parathyroid hormone (PTH), thyroid stimulating hormone (TSH), and free thyroxine (free T4). (Direct bilirubin will be assessed only if total bilirubin ≥ 2.0 mg/dL. Vitamin B12, folate, and RPR is

collected only at Baseline and as part of the comprehensive medical follow-up evaluation to rule out other causes of dementia).

- Hematology including red blood cells, white blood cells, neutrophils, eosinophils, basophils, lymphocytes, monocytes, hemoglobin, hematocrit, platelets, and HbA1c. (HbA1c is collected only at Baseline.)
- Urinalysis including pH, specific gravity, glucose, and nitrite. (Protein and blood values will not be summarized but will be included in the listings.)

For each laboratory parameter, the following will be displayed for each scheduled time point (each visit and end of study).

- Summary statistics (n, mean, SD, median, minimum, and maximum) by treatment group and overall for the actual values and change-from-Baseline values.
- Shift tables for the change from Baseline to each post-baseline time point will be presented. For these tables each subject will be categorized as low, normal, or high for the baseline value and low, normal, or high for each post-Baseline time point, according to the central laboratory reference ranges. The number of subjects in each of the combinations of shifts will be presented.
- Markedly abnormal values for laboratory parameters, as defined in [Appendix A](#), will be summarized by treatment group and overall. The number and percentage of subjects with MAV values observed post-Baseline in each of the applicable laboratory parameters will be presented.
- Number and percentage of subjects with elevated liver enzyme lab values will be presented using the criteria described in the protocol.

Subject mappings will be provided for markedly abnormal lab values and elevated liver enzyme lab values.

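### Laboratory, ECG, vital-sign and C-SSRS values more than 7 days after last dose are listed but not tabulated, so every on-schedule follow-up C-SSRS and any later liver test misses the safety tables, while AEs are summarised to 30 days

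*SAP*

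**What the plan says.** SAP 9.1.3 gives adverse events one cut-off: "Adverse events that start more than 30 days after the last dose of double-blind study medication" are listed but left out of the summaries. SAP 9.14.1 defines treatment-emergent events the same way, with onset "within 30 days after receiving the last dose of study drug". All other measured data get a shorter cut-off: "For efficacy and other safety data, data that are obtained more than 7 days after the last dose of double-blind study medication" "will be listed, but excluded from summaries and analyses". The only exception in that paragraph is for adjudicated MCI or AD dementia events in the time-to-event analyses. SAP 9.14 applies these conventions to safety: "Conventions for the definition of baseline values and visit windowing are provided in Section 9.1.3".

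The protocol asks for safety data beyond that point. In Protocol 9.1.17 (Table 9.c) the C-SSRS is scheduled at "Visit 3, every 6 and 12 month visit after randomization, EoS/EW Visit, and follow up visit". Protocol 9.3.7 and Appendix A place that follow-up contact 2 weeks after EoS/EW. For liver signals, Protocol 7.4 says that "study medication should be discontinued immediately with appropriate clinical follow-up, including repeat laboratory tests" must follow, continuing until the profile is normal.

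On the table side, SAP 9.10 summarises C-SSRS by visit, with positive reports and shifts at baseline and during treatment. SAP 9.14.2 counts subjects with markedly abnormal post-baseline values and adds: "Number and percentage of subjects with elevated liver enzyme lab values will be presented using the criteria described in the protocol".

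**The concern.** The follow-up C-SSRS and the liver tests after a stop are collected because the protocol wants to know what happens after the drug is withdrawn. The 7-day rule then takes most or all of them out of the tables, and the SAP gives no reason for 7 days here against 30 days for adverse events. The exclusion is triggered by stopping drug, so it bears on the subjects in whom a late abnormality would be of most interest.

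At stake is the completeness of the suicidality and liver tables in a trial of cognitively normal people, for whom Protocol 4.2.2 sets a high safety threshold. No primary or key secondary efficacy result depends on it.

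**Working it through.** **Inputs.** Cut-off for other safety data: excluded if visit date minus last-dose date is greater than 7 (SAP 9.1.3). AE cut-off: 30 days (SAP 9.1.3, 9.14.1). Follow-up contact: EoS/EW plus 14 days (Protocol 9.3.7). Assumption: the last dose is no later than EoS/EW, because study drug is collected at that visit (Protocol Appendix A). The SAP states no figure to reproduce.

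**C-SSRS.** Let g be the days from last dose to EoS/EW, with g at least 0. EoS/EW falls on day g and the follow-up C-SSRS on day g + 14.

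| g | EoS/EW values tabulated (g ≤ 7) | Follow-up C-SSRS day | Kept at 7 days | Kept at 30 days |
|---|---|---|---|---|
| 0 | yes | 14 | no | yes |
| 7 | yes | 21 | no | yes |
| 8 | no | 22 | no | yes |
| 16 | no | 30 | no | yes |
| 17 | no | 31 | no | no |
| 30 | no | 44 | no | no |

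The smallest possible value is 0 + 14 = 14, which exceeds 7, so every on-schedule follow-up C-SSRS is excluded. SAP Table 9.b lists the C-SSRS among the efficacy variables, but this makes no difference, because the 7-day rule covers efficacy and other safety data alike. SAP Table 9.a has no follow-up window either. Moving to 30 days would not fully solve it: g + 14 ≤ 30 requires g ≤ 16.

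**Liver tests.**
- Every immediate-stop condition in Protocol 7.4 requires ALT or AST above 3xULN. SAP Appendix A uses the same limit for a markedly abnormal ALT or AST.
- The tables count subjects, so a subject stopped on these grounds is normally already in the ALT/AST rows. Later exclusions do not remove that count.
- The first repeat is due within 7 days (Protocol 7.4, 9.1.8). A stop on the day of the finding puts that repeat inside the window.
- The remaining gap can be shown by example. Drug is stopped for ALT above 8xULN, and bilirubin first passes 2xULN on day 10 after last dose. Since 10 > 7, the subject appears in the ALT row but not in the bilirubin row (above 2.0 mg/dL in SAP Appendix A), nor under the combined ALT/AST-plus-bilirubin criterion. At 30 days both would count, since 10 ≤ 30.

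**Laboratory, ECG and vital signs at early withdrawal.** None is scheduled at the follow-up contact (Appendix A), so the rule affects only EoS/EW visits with g of 8 or more, and unscheduled tests. The documents give no distribution of g. The share excluded could be none (all g ≤ 7) or all (all g > 7), so no percentage is offered.

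**A second ambiguity.** SAP 9.14.2 introduces its laboratory displays as being for each scheduled time point, yet describes markedly abnormal values simply as post-baseline. Whether an unscheduled liver repeat counts is therefore unclear whatever the day limit.

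**The case against.** The strongest reply has four parts.

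**The data are kept.** A reader might infer that these values are lost. They are not. SAP 9.1.3 lists them, SAP 9.1.2 carries all raw data into the derived datasets, and SAP 9.14.2 lists all laboratory data with flags, markedly abnormal values separately, and the liver-function eCRF pages. This stands: the issue is tabulation only.

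**Subjects stopped for toxicity are not missing.** A reader might infer that those who stop for liver toxicity drop out of the abnormality tables. The documents do not support this, because the value that triggers the stop normally puts the subject in the ALT/AST rows already.

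**The AE tables are a second route.** ALT/AST above 3xULN on two occasions is an AE. With bilirubin above 2xULN and no alternative cause it is an SAE (Protocol 10.2.3). Suicide, attempts and intention with a definite plan are SAEs, and lesser ideation is a non-serious AE (Protocol 9.1.16). These fall under the 30-day window, and hepatic effects are a summarised AESI. This stands in large part. It is not equivalent, because it depends on an event being recorded and, for the combined liver criterion, on a judgement about cause; the tables are objective counts.

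**A 7-day on-treatment window is a legitimate choice.** It applies to both arms, and a C-SSRS at day 14 does not belong in a during-treatment count. SAP 9.14.3 and 9.14.5 likewise define abnormal vital-sign and ECG counts for the double-blind treatment period. This also stands. It argues for a separate post-treatment row, not for leaving the assessment out of every table.

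**Conclusion.** The point holds as a gap in tabulation. For the follow-up C-SSRS it is complete: every on-schedule value is at least day 14 and enters no summary table. For liver tests it is narrow: a bilirubin rise, a later peak or a first abnormality appearing more than 7 days after last dose. Late early-withdrawal values are affected in the same way, to an unknown extent.

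This rests on the last dose being on or before EoS/EW and on the call being made on schedule. Appendix A gives the follow-up contact no visit window, so a call made a week or more early could fall inside 7 days. Subjects entering the extension have no call, and for those who withdraw consent the contact is not entered in the eCRF (Protocol 9.3.7), so the C-SSRS point concerns the remainder.

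Protocol 13.1.6 plans to tabulate potentially clinically significant values with no 7-day limit, and SAP 9.17 does not mention the cut. That alone is not a contradiction, since the protocol leaves detail to the SAP, but it is a reason to state the rule openly. The change is a worthwhile, inexpensive improvement; the trial's conclusions on efficacy do not turn on it.

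**What to change.** Amend SAP 9.1.3, 9.10 and 9.14.2 together:

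- **C-SSRS.** Show the follow-up assessment as its own post-treatment row in the positive-report and shift tables, exempt from any limit on days after last dose. The exemption is needed because a 30-day limit would still drop it when EoS/EW is more than 16 days after last dose.
- **Laboratory abnormality counts.** In the markedly-abnormal and elevated-liver-enzyme tables, include all post-baseline values, scheduled and unscheduled, up to 30 days after last dose, matching the TEAE window. Flag values after day 7 as off-drug.
- **By-visit means.** Keep the 7-day rule.

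The cost is SAP wording and table programming on data already collected, with no new assessments and no change to subject management. The downside is that a few off-drug values enter the abnormality counts; the flag lets a reader separate them.

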Following a significant finding for the primary efficacy endpoint, a sequential testing hierarchy will test the rate of cognitive decline endpoint first and then, if significant, proceed to testing the impairment of functional abilities using the functional impairment assessment ADCS ADL-PI As for the primary analysis, these key secondary endpoints will be tested at the $\alpha = 0.01$ level. The analyses for these endpoints will be analysis of covariance (ANCOVA) for change from baseline using mixed models repeated measures (MMRM).

The other secondary endpoints will be analyzed using ANCOVA, logistic regression, survival analyses, or chi-squared tests as appropriate to the data. As for the primary analysis, the secondary endpoints will be tested at the $\alpha = 0.01$ level.

The primary endpoint in this study is event-based and subjects who discontinue from the study prior to having the event will be censored in the primary analysis. However, for completeness, follow-up information will be collected on as many subjects as possible, including the reason for discontinuation. For the continuous variables such as the composite scores, mixed models repeated measures using all available data will be used to evaluate changes over time.

The rules for handling missing items from each of the scales are designed so that as much data as possible can be used in the analyses, yet with reliable information, when calculating total scores.

Missing data may occur in the course of the study or may be due to drop-out. With regard to neuropsychological data collection within the study, missing data can occur under several scenarios. In an interview setting administration of some portions of the test battery may be precluded by tester error or factors attributable to the patient (illness, refusal, or other problems). Neuropsychological technicians will be trained to avoid missing data whenever possible. In the event that an item or a test is missing, technicians will be trained to record the reason for missing data. When tests are scored, the reason for missing data will be coded in a uniform, standardized manner across sites. Test scores will be prorated wherever possible.

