9.9.6 Analysis of Key Secondary Variables

The change from baseline in cognitive battery composite score will be analyzed as a continuous variable by study visit using MMRM (mixed model for repeated measures) analysis of covariance with treatment, gender, center, visit, and treatment-by-visit interaction as fixed, categorical effects and education, age, baseline composite score, and baseline composite score-by-visit as continuous, fixed covariates. The effect at each time point for each treatment is allowed to vary freely, and an unstructured covariance matrix will be used to model the within-subject errors. The Kenward-Roger approximation will be used to estimate denominator degrees of freedom. Based on a Missing at Random (MAR), this analysis will be performed using observed case data only.

The SAS code for the MMRM analysis will be as follows:

```
Proc mixed data=all;
```

- class visit treat center gender subject;
- model Change = Baseline Baseline*visit treat center gender education age visit visit*treat /solution ddfm=KenwardRoger;
- repeated visit/subject=subject type=UN;
- lsmeans visit*treat / cl pdiff.

In the above model, Baseline is the baseline value and Change is the change from baseline value.

Similarly, the change from baseline in ADCS ADL-PI ADL total score will be analyzed as a continuous variable by study visit using MMRM, where the ADCS ADL-PI ADL total score Baseline, gender, education, and age will be used as the covariate adjustments in the MMRM.

Key secondary endpoints will be analyzed (including reporting mean differences, CIs, and p-values) using the FAS subjects in the primary efficacy population (high-risk, non-Hispanic/Latino subjects) using a 0.01 significance level.

Although change-from-baseline endpoints will be assessed at all visits, the primary time frame for purposes of efficacy analysis is the change from baseline to Month 48 (Year 4).

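### SAP 9.1.3 drops continuous efficacy scores taken more than 7 days after last dose, although the protocol specifies MMRM on all available data, and SAP 9.17 does not declare the change

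*SAP*

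**What the plan says.** **SAP 9.1.3** sets a window for efficacy and non-adverse-event safety data. Anything "data that are obtained more than 7 days after the last dose of double-blind study medication" goes into listings but stays out of summaries and analyses. A note in the same section makes the reach explicit: the window decides what is "included/excluded from the summary statistics and formal statistical analysis tables for a given efficacy endpoint". The note gives one exemption: adjudicated events of MCI due to AD or AD dementia "will be included in the time-to-event analyses, without regard to the date of last dose of double-blind study medication".

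**Protocol 13.1.3** says that for continuous variables such as the composite scores, "mixed models repeated measures using all available data will be used to evaluate changes over time". It attaches no on-treatment condition.

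**SAP 9.9.6** analyses the two key secondary endpoints, the cognitive composite and the ADCS ADL-PI, by MMRM under missing at random. It says that "this analysis will be performed using observed case data only" and makes Month 48 the main time point. SAP 9.9.8 places both endpoints after the primary test in a fixed sequence at 0.01.

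**SAP 9.17**, the section for changes from the protocol's analysis plan, lists only the academic-degree item.

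**The concern.** An EW visit is held because the subject is leaving. Protocol 7.5 plans only telephone contact for subjects who stop study drug early, so the EW assessment is normally the last cognitive or functional score they give. MMRM under missing at random relies on the observed scores to account for who leaves. The score nearest to withdrawal carries most of that information, so leaving it out weakens the assumption if declining subjects tend to leave.

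That is plausible on the sponsor's own account. The Amendment 6 summary gives, as a reason for easing follow-up visits, that subjects near the endpoint trigger repeatedly and tire of the study. Protocol Table 7.a requires subjects who start an acetylcholinesterase inhibitor or memantine to be discontinued.

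The testing sequence also mixes data rules. Its first test counts off-drug events, and its second and third omit off-drug scores. The FAS in SAP 9.3 analyses subjects as randomized, while this window makes the continuous endpoints on-treatment without saying that this is the target of estimation.

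**Working it through.** **1. Does the window reach the key secondary models?** Yes. They are efficacy analyses, the note covers formal analysis tables, and the only exemption is for adjudicated events.

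**2. Do other planned analyses use the excluded scores?** No.
- The pattern-mixture analysis in SAP 9.9.6 imputes values after discontinuation from control-arm data. It treats the excluded scores as missing.
- SAP 9.9.9 leaves unscheduled-visit values out of these analyses, so scores from a comprehensive medical follow-up visit cannot stand in.
- SAP 7.2.1.2 defines additional endpoints at 6-month visits and at EoS/EW, so EW scores were meant to be analysed.

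**3. Which scores are lost?** Three conditions must all hold:
- the EW visit is attended;
- it is more than 3 months after the last scheduled visit (Protocol Appendix A, footnotes i and u, for the battery and the ADCS ADL-PI);
- it is more than 7 days after last dose.

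Appendix A sets no 7-day limit on the EW visit. Its footnote o omits PK samples for subjects off drug for 3 or more days, so some off-drug EW visits are expected.

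**4. Is a lost score only a duplicate?** Normally not. SAP Table 9.a changes window at the midpoint between visits. For example, 183 + 91 = 274, the first day of the Month 12 window, and 1278 + 91 = 1369, one day before the Month 48 window opens at 1370. An EW battery more than 3 months after an on-time visit therefore usually stands alone in the next window.

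**5. How many subjects?** Inputs are 12% annual dropout and 2,346 high-risk subjects (SAP 8.0), or 2,940 as estimated after Amendment 5 (SAP 6.4).
- The plan's own figure reproduces: 1 − 0.88^5 = 47.2%, against 47% stated.
- Withdrawals by Year 4: 1 − 0.88^4 = 40.0%, or 939 of 2,346 (1,177 of 2,940).
- Assumption A: withdrawals are uniform within each 6-month interval, so half come more than 3 months after a visit. 40.0% × 0.5 = 20.0%, or 470 of 2,346 (588 of 2,940). This also assumes that every withdrawal attends an EW visit, which makes it a ceiling under A.
- Assumption B: a share s of those visits falls more than 7 days after last dose. The documents do not give s.

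| s | % of subjects | of 2,346 | of 2,940 |
|---|---|---|---|
| 0% | 0 | 0 | 0 |
| 25% | 5 | 117 | 147 |
| 50% | 10 | 235 | 294 |
| 75% | 15 | 352 | 441 |
| 100% | 20 | 470 | 588 |

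**6. Direct effect at Month 48.** An EW battery is the only Month 48 value for withdrawals between about day 1370 (3.75 years) and day 1461 (4 years): 0.88^3.75 − 0.88^4 = 0.619 − 0.600 = 1.9% of subjects. With s from 25% to 75%, 1.9% × 0.25 to 1.9% × 0.75 is about 0.5% to 1.5%. The other excluded scores reach the Month 48 estimate only through the MMRM covariance.

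**The case against.** The strongest defence is that the rule is deliberate and narrow. The SAP's note separates events, counted regardless of dosing, from scores, taken on treatment. With no cognitive testing scheduled after drug is stopped, an on-treatment target for scores can be defended. Protocol 13.1 leaves analysis detail to the SAP, and a footnote to Protocol Table 7.a already allows battery data to be censored when a concomitant medication is not stable. The pattern-mixture analysis addresses drop-out that is not at random, and EoS/EW data still feed the adjudication of primary events (SAP 9.9.4).

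Part of this stands. On-treatment scores are a legitimate target, and the pattern-mixture analysis is a real safeguard. But neither the delegation nor the medication footnote authorises a general on-treatment cut against an explicit statement that all available data will be used. Such a target would need to be justified and declared, and it is neither.

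A reader might go further in three ways that the documents do not support:
- **That all early withdrawals lose their last score.** They do not. EW scores within 7 days of last dose are kept, withdrawals within 3 months of a scheduled visit need no EW battery, and all on-drug scheduled scores stay in.
- **That 5% to 15% is an estimate.** It rests on an assumed share and full EW attendance. Some subjects are lost to follow-up or die, and Protocol 7.5 asks only for an effort to complete the EW procedures. If the last-dose date is missing, SAP 9.1.3 takes the earliest of several dates, including last visit and drug return, which can place last dose at the EW visit and keep the score.
- **That the Year 4 means are biased in a known direction.** The rule is the same in both arms, and the documents give no SD, no gap between dose and visit, and no scores by reason for withdrawal.

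**Conclusion.** The conflict between the two documents is real, undeclared, and reaches the two key secondary tests. Its size is bounded but not known. Between 0% and 20% of high-risk subjects lose a score by Year 4, assuming 12% annual dropout and uniform withdrawal within intervals. With 25% to 75% of the relevant visits beyond 7 days, the loss is at most about 5% to 15%. The direct loss at Month 48 is about 0.5% to 1.5% under the same assumptions, so most of any effect on the Year 4 tests is indirect. Dropping these scores weakens the missing-at-random assumption if decliners leave, but neither the size nor the direction of bias can be computed. The primary efficacy and biomarker analyses are unaffected, because adjudicated events are exempt.

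**What to change.** In SAP 9.1.3, lift the 7-day restriction for continuous efficacy endpoints. State in SAP 9.9.6 and 9.9.9 that the main MMRM for the key secondary and additional continuous endpoints uses all observed post-baseline scores at scheduled and EoS/EW visits, whatever the last-dose date, as the protocol specifies. Keep the 7-day version as a sensitivity analysis labelled on-treatment. Report by arm how many scores the restriction removes.

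The cost is a wording change and one extra model run per endpoint. The downside is that a few off-drug scores may slightly dilute an on-drug effect, which the retained analysis would show. If the sponsor prefers on-treatment scores as the main analysis, the reason should be given and the departure from Protocol 13.1.3 declared in SAP 9.17, with the all-data MMRM shown beside it.
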